## LIMITATIONS OF THE STUDY

Despite the prospective design of the study, there are certain limitations to take into account during its development and analysis of results. Among them, the following stand out:

1.- Possible existence of confounding variables that have not been taken into account in the study approach, that are unknown or not measurable or suitable for collecting and that influence the results.

To solve this possible limitation, an extensive bibliographic search has been carried out and all the easily accessible variables that can influence the result in a global way have been included.

2.- Possible limitations in the collection of information. Being a multicenter study that includes the collection of a large number of variables, there is the possibility of a partial collection of all the information required in each included case.

To reduce this limitation, the collection of information is proposed in the most objective way possible, filling in all the variables proposed to be studied and carrying out periodic supervision and evaluation of the quality and quantity of the data entered in each center. Once all the data has been collected and added to the database according to the instructions described, the database will be sent to the study coordinators, who will evaluate its content and review again the quality and quantity of the data entered, being able to notice errors that require a correction by the researchers responsible for each center.

3.- Another possible limitation of the study is the low incidence of the pathology studied in our environment, which requires a long period of time to achieve an optimal sample size.

As a solution to this limitation, a multicenter study has been proposed, trying to achieve the greatest possible collaboration and participation of all the centers at the national level, in order to achieve an adequate sample size in the expected data collection time. .

4.- Another possible limitation of the study could be the differences in the surgical technique and the specific perioperative management protocols of each center, which, being different and particular in each one of them, would facilitate a wide variability in the management of the cases. However, the purpose of the study is to create a predictive model that is universal and based on objective clinical and analytical variables, in order to obviate these differences between centers and with the ability to be applied in each of them with the same effectiveness.

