### 4.- Sample size

The purpose of the study is to recruit as many patients as possible from all national centers who wish to participate.

For an alpha error of 5% (95% confidence) with a precision of 3% and estimating a number of patients with major complications (including AF) around 30%, the calculation of the sample size yields a total of 847 patients. However, the final sample size may be smaller depending on the proportion of complications detected and the statistical and artificial intelligence models to create the predictive model will be adapted to the event rate provided by the recruited sample.

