## **6.- Intervention**

The patient will undergo the indicated surgical intervention depending on whether it is an esophageal or gastric neoplasm, with curative intent with or without prior neoadjuvant treatment. Surgical intervention and postoperative care will be carried out in each of the centers of the national territory that commit to participate according to their usual clinical practice. Thus, the perioperative management and care protocol will be that of each center without the need to apply exceptional measures (beyond the control of the clinical and analytical variables of this study) or a homogeneous protocol in all the participating centers.

The analysis and control of the preoperative clinical variables must be carried out the day before or the same day of the surgical intervention prior to it.

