### 2.- Data análisis

The statistical study will be carried out with the help of the SPSS® version 23.0 software for Windows, using the MATLAB® programming environment for the preparation of the predictive model based on artificial neural networks (ANN).

In the first place, a descriptive analysis will be carried out, both of the sociodemographic and clinical variables, as well as of the analytics and the results of the study.

To describe the quantitative variables that follow a normal distribution, the mean and standard deviation will be used, and the median and interquartile range for those that do not follow a normal distribution, as well as histograms with normality curves for their graphical description.

For the qualitative variables, frequencies and percentages will be used, using bar graphs and/or sectors for the graphic description of those with greater relevance.

A univariate study will be performed to relate the variables studied with the appearance of AF and major postoperative complications. For this, different tests will be used depending on the variable to be studied:

- a) Normal categorical variables: Chi-square test or Fisher's exact test.
- b) Normal continuous variables: Student's t-test.
- c) Non-normal continuous variables: Mann-Whitney U test.

In the results obtained from the univariate study, those variables that show a  $p < 0.1$  after the application of the corresponding tests will be considered as related or candidates to predict AF or major

complications. This value will be considered more conservative, different from the conventionally accepted value of 0.05, with the intention of not ruling out potential variables that could have some influence on the results of the study.

Once the univariate study has been completed, a multivariate study will be carried out, using the logistic regression (RL) method. To do this, a recoding of the variables will be carried out, transforming the categorical variables into dummy variables. It will be verified that the variance inflation factor (VIF) is less than 2 in all cases, thus ruling out important problems of collinearity between the variables.

On the other hand, a predictive model based on artificial neural networks (ANN) will also be developed, using a Multilayer Perceptron, a multilayer neural network of forward connections, without recurrent connections and supervised learning.

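### The model is meant to work equally well in every centre, but the analysis has no centre term, no clustering adjustment and no comparison across centres

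*Combined protocol and SAP*

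**What the plan says.** Section 6 (Intervention) states that "the perioperative management and care protocol will be that of each center", with no common protocol required. Item 4 of the Limitations section acknowledges that this produces wide variability. Its answer is that the model will rest on objective clinical and laboratory variables, "in order to obviate these differences between centers and with the ability to be applied in each of them with the same effectiveness".

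The Data analysis section screens each candidate with "Chi-square test or Fisher's exact test" for categorical variables and Student's t or Mann-Whitney tests for continuous ones, keeping those with p<0.1. Then "a multivariate study will be carried out, using the logistic regression (RL) method", and a multilayer perceptron is built alongside. No centre term, random effect, cluster-robust variance, stratification or validation by centre is named. Centre is not among the variables listed in section 8.2.

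Section 4 (Sample size) states that "the calculation of the sample size yields a total of 847 patients" and mentions no design effect. Item 5.8 of the Schedule promises an evaluation of the released tool on new data, without a metric, a criterion or a breakdown by centre.

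**The concern.** Patients treated in one centre share technique, postoperative care and leak work-up, so their outcomes are likely to be correlated. Two consequences follow.

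The first concerns the screen. A test that treats patients as independent understates the variance for a predictor that itself clusters by centre. Surgical approach, anastomosis type, fluorescence assessment, conditioning of the gastric conduit and pyloric procedure are all collected, and each plausibly reflects centre habit. Such variables can pass p<0.1 more often than intended by standing in for differences between centres.

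The second concerns the stated purpose. Objective predictors do not remove differences between centres in baseline leak risk or in detection. The Introduction reports leak rates of 0-34% across series and links the spread to the lack of an agreed definition and diagnostic method. Section 8.2 fixes one grading for all centres, but endoscopy and CT are only recorded as yes or no, and no common work-up is required. Grade I leaks, which may need no specific treatment, count as events, so ascertainment can depend on imaging habits. A pooled model could then give risks that are too high in some centres and too low in others. The tool is intended to inform decisions about individual patients, and nothing specified would reveal this.

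**Working it through.** **Inputs from the documents.** Planned size 847 (section 4); screening threshold p<0.1 (Data analysis).

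**Inputs assumed.** Number of centres K = 20 to 60; ICC of the outcome = 0.01 to 0.05. The documents give neither.

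**The plan's own figure.** The single-proportion precision formula with 30%, 3 points and 95% confidence gives n = 1.96² × 0.30 × 0.70 / 0.03² = 896.3, so 897. The stated 847 is not reproduced. That is a separate matter; 847 is used below only as the planned count.

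**Predictor constant within centre.** With m = 847/K, the design effect is DE = 1 + (m − 1) × ICC, the effective n is 847/DE, and the true size of a nominal two-sided 10% test is 2 × [1 − Φ(1.645/√DE)].

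| Centres | m | ICC | DE | Effective n | True size |
|---|---|---|---|---|---|
| 60 | 14.1 | 0.01 | 1.13 | 749 | 12% |
| 60 | 14.1 | 0.05 | 1.66 | 511 | 20% |
| 20 | 42.4 | 0.01 | 1.41 | 599 | 17% |
| 20 | 42.4 | 0.05 | 3.07 | 276 | 35% |

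For the last row: 1 + 41.35 × 0.05 = 3.07; 1.645/1.751 = 0.939; 2 × (1 − 0.826) = 0.35.

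**Predictors that cluster partly or not at all.** The formula does not cover these, so the t-test at p<0.1 was simulated with no true predictor effect and a random centre intercept. There were 840 patients (42 centres of 20, or 21 of 40), an outcome rate of 10% or 30%, an ICC of 0.02, 0.05 or 0.10 on the latent logistic scale, and 3000 runs per setting.

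| Share of predictor variance between centres | True error of the screen |
|---|---|
| 100% (constant within centre) | 0.125 to 0.37 |
| 30% | 0.10 to 0.21 |
| 10% | 0.10 to 0.15 |
| 0% | 0.09 to 0.11 |

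The ICC scale and range differ from those in the formula, so the two tables agree in pattern rather than cell by cell. Inflation grows with the between-centre share of the predictor and is absent when that share is zero.

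**Could single centres be compared directly?** Using the Hanley-McNeil standard error at an assumed AUC of 0.80, the 95% half-width is about 0.24 for 20 patients with 6 events (30%). It is about 0.27 for 40 patients with 4 events (10%). Raw single-centre AUCs would be mostly noise, so an assessment across centres has to pool.

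**The case against.** The strongest reply is that most of the intended predictors are measured on each patient. The daily set in section 8.2.2 (vital signs, leukocytes, CRP, albumin, IL-6 and others) should vary mainly within centres, where the simulation shows the screen close to nominal. Even the surgical variables need not be constant within a centre, since they can depend on the operation and a centre may contribute both oesophagectomies and gastrectomies. The p<0.1 threshold is deliberately liberal and a multivariable step follows, so an extra variable passing is milder than a false confirmatory result. All of this stands, and it limits the size of the problem.

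It can also be said that leaving centre out of the prediction equation is defensible, because a new centre has no estimated intercept. That is correct for the equation. It does not excuse ignoring centre in the inference or in the validation.

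A reader might infer more than the documents support:

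- **That all the screening p-values are wrong.** Only those for centre-clustered predictors are affected.
- **That the effective sample size falls close to the number of centres.** Under the assumptions above it is 276 to 749, against 20 to 60 centres.
- **That the plan asserts equal effectiveness as a result.** Item 4 of the Limitations states it as a purpose.
- **That the aim will never be tested.** Item 5.8 of the Schedule promises a later evaluation. What can be said is that no comparison across centres is specified.

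**Conclusion.** The point holds in limited form. The plan aims for equal performance in each centre while accepting that care differs, yet it specifies no centre term, clustering adjustment or validation by centre. The aim is therefore not assessed by any specified analysis; this part needs no assumed figures.

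The effect on the screen does rest on assumptions. With 20 to 60 centres, 847 patients and an ICC of 0.01 to 0.05, the nominal 10% error is about 12% to 35% for a predictor constant within centre. It is smaller with partial clustering and near nominal for predictors that vary only within centre. How strongly the named surgical variables cluster is unknown, so the upper figure should not be read as typical. A model can still be built as planned, but its universality could not be supported.

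**What to change.** 1. Name the centre code as an analysis variable. It is not listed in section 8.2, but database passwords are issued per centre and authorship order depends on cases contributed, so it should be recoverable.
2. Use centre-clustered standard errors or a centre random intercept for the screening tests and the logistic inference.
3. Evaluate both the logistic model and the neural network by internal-external validation, leaving out one centre, or one group of small centres, at a time.
4. Report pooled discrimination and calibration with an estimate of between-centre heterogeneity, rather than raw single-centre AUCs.
5. Limit any statement of equal effectiveness to what this validation shows. A random intercept alone does not cure miscalibration in a centre that was not in the data.

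The cost is additional SAP text and standard routines, with no new patient data. Intervals will be somewhat wider, and the reported performance is likely to be less favourable.

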## ETHICAL AND LEGAL ASPECTS

This study will be carried out under the following ethical considerations and based on current legal regulations.

### 1.- Ethical considerations

The nature and prospective and observational nature of the study do not imply the application of techniques or procedures that are not contemplated in the current Clinical Practice Guidelines, recommendations endorsed by scientific societies and consensus of experts accepted and used routinely and globally regarding clinical management. (diagnosis and therapeutic) of these patients.

### 2.- Regulations and medical-legal aspects

During all the analytical stages of the study, the data collected will be used anonymously in accordance with current regulations on confidentiality and data protection, guaranteeing the protection of personal data according to Regulation (EU) No. 2016/679 of the European Parliament and of the Council of April 27, 2016 on Data Protection (RGPD) (28), maintaining professional secrecy at all times regarding the data of the patients included in the study, which will be scrupulously handled.

This study will be carried out following the current regulatory requirements, respecting the codes and standards of good clinical practice and guaranteeing the rights of patients, as well as the basic ethical principles (Declaration of Helsinki approved by the World Medical Assembly in its Fortaleza version in 2013 (29) and the Oviedo Convention of 1997) (30). The rights, safety, and welfare of study patients will take precedence over the interests of science.

Thus, each patient included in the study must previously grant her consent by signing a specific informed consent prepared for this purpose. The legal representative will give their informed consent in the event that the patient is not legally competent.

The collection of patient data will be methodical and exhaustive. The data of each patient will be codified, anonymized, included and managed in the database designed for it. Once the study has been completed, the data will be kept on file for the maximum legally established time (15 years) to ensure possible audits and controls. After this period, they will be deleted.

Biological samples will not be obtained for this study, although data derived from routine blood tests and other healthcare diagnostic tests and used in routine clinical practice recorded in your medical record will be collected.

The study will begin once this project is evaluated, approved and authorized by the Research and Ethics Committee of the different participating hospitals.

### 3.- Insurance

Due to the characteristics and design of the study, insurance coverage is not considered necessary.

## **CONFLICT OF INTERESTS**

The researchers assure that there is no type of conflict of interest that could compromise the validity of the results.

### Anexo 3.- Carta de presentación e invitación a participar en el estudio

Querid@ compañer@;

Como bien sabes la fuga anastomótica en la cirugía esofagogástrica es una de las más temidas complicaciones y, a pesar de los múltiples avances realizados para disminuir su incidencia, ésta aún sigue siendo considerable. Además, su aparición durante el postoperatorio de nuestros pacientes se asocia a un incremento considerable de la mortalidad, estancia hospitalaria y deterioro grave de su estado funcional. Por todo ello, además de las múltiples medidas que aplicamos para prevenir su aparición, es de vital importancia establecer un diagnóstico lo más precoz posible, con el propósito de aplicar un rápido y adecuado tratamiento en cada caso, lo cual disminuye de forma significativa la mortalidad asociada a esta complicación.

Así, con el propósito de crear un modelo predictivo que permita identificar los pacientes con un elevado riesgo de fuga anastomótica durante el postoperatorio de una cirugía esofagogástrica ha nacido el **estudio PROFUGO** (Modelo **PR**edictivo para el Diagnóstico Precoz de la **FUG**a anastomótica tras Esofaguetomía y Gastrectomía). El estudio tiene un diseño **prospectivo y multicéntrico** y pretende, mediante el análisis de diferentes variables clínicas y analíticas recogidas durante el postoperatorio de estos pacientes, elaborar con ayuda de métodos de **inteligencia artificial** una herramienta que permita identificar casos con un elevado riesgo de fuga anastomótica. Con ello, en los pacientes identificados por el modelo con un riesgo elevado, se podría actuar en consecuencia e indicar las exploraciones complementarias que se consideren adecuadas para obtener un diagnóstico precoz, evitando así un mayor deterioro del paciente y una posible situación séptica en estados más avanzados.

